### **Safety issues (require expedited reporting)**

Significant Safety Issue (SSI): A safety issue that could adversely affect the safety of participants or materially impact on the continued ethical acceptability or conduct of the trial.

### **Urgent Safety Measure (USM)**

A measure required to be taken in order to eliminate an immediate hazard to a participant's health or safety.

## **6.3 Capturing and eliciting adverse event/reaction information**

Adverse events and adverse reactions (non-serious and serious) will be captured from the time of administration of the medication until 30 days following the final dose (fifty days after commencement of the trial) and will be followed until resolution or stabilisation.

At every trial visit participants will be asked "How have you felt since your last visit?" in order to elicit any medically related changes in their well-being. They will also be asked if they have been hospitalised, had any accidents, used any new medication or changed concomitant medication regimens. In addition, AEs will be documented from physical examination

---

findings, clinically significant lab results or other documents (including participant diaries and correspondence from their primary care physician) that are relevant to participant safety. This will be recorded in the patient's medical record as well as communicated with members of the research team.

#### **6.4 Documentation of AEs**

For the purposes of this trial the investigator is responsible for recording all Adverse Events, regardless of their relationship to trial drug, with the following exceptions:

- Conditions that are present at screening and do not deteriorate will not be considered adverse events.
- Abnormal laboratory values will not be considered adverse events unless deemed clinically significant by the investigator and documented as such.

The AE will be described in the source documents (e.g. medical record or trial shadow file) and captured on the CRF and will include:

- A description of the AE
- The onset date, duration, date of resolution
- Severity (mild, moderate or severe – what is the impact on the participant's daily life?)
- Seriousness (i.e. is it an SAE?)
- Any action taken, (e.g. treatment, follow-up tests)
- The outcome (recovery, death, continuing, worsening)
- The likelihood of the relationship of the AE to the trial treatment (Unrelated, Possible, Probable, Definite)

Changes in the severity of an AE will be reported. AEs characterised as intermittent will be documented for each episode. All AEs will be followed to adequate resolution, where possible.

#### **6.5 Assessing the seriousness of a participant's AE**

The seriousness of an AE will be assessed by an investigator according to the definition in in the preceding section on definitions with the following exception(s):

- Hospitalisation due to progression of disease will not be considered an SAE for the purposes of this trial.
- \* The severity and relationship of an AE will be assessed as per the following section.
- \*\* The seriousness of an AE will be assessed by an investigator according to the definition in Section 8.1, with the following exceptions:
- Hospitalisation due to progression of disease will not be considered an SAE for the purposes of this trial.
  - Elective surgery planned at the time of enrolment.

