## PROTOCOL SYNOPSIS

TITLE	Can Vitamin C prevent Complex Regional Pain Syndrome in lower limb trauma? A double-blinded randomised, controlled feasibility study.
TRIAL DESCRIPTION	
This is a randomised controlled feasibility trial conducted at five sites:
 

• Peninsula Health

• Frankston Private Hospital

• Holmesglen Private Hospital

• Cabrini Brighton Private Hospital

• Beleura Private Hospital

 
The trial will recruit patients who present for elective and emergency surgery of the foot and ankle. Patients will be randomised into two groups – placebo and 500mg vitamin C. Patients will then be assessed at regular intervals up to six months post injury/surgery to determine whether chronic regional pain syndrome was diagnosed.

OBJECTIVES	
Primary objective – to determine if the proposed protocol is feasible with regards to:
 

• Recruitment capability

• Data collection procedure

• Suitability of intervention

• Resource availability

• Participant response

 
Secondary objectives:
 

1. to determine if vitamin C prevents CRPS in patients with lower limb extremity trauma in a dose-response manner

2. to determine the incidence of CRPS in lower limb extremity trauma and elective surgery.

3. To determine the demographics and characteristics of patients who develop CRPS of the lower limb

OUTCOMES AND OUTCOME MEASURES	
The outcome is development of CRPS at any stage following trauma or surgery within the six-month time frame. The outcome measure is the validated Clinical Diagnostic Criteria for CRPS, also known as the ‘Budapest Criteria’(1).

TRIAL POPULATION	
Adult patients (defined as aged 18 and over) who undergo elective or trauma surgery on their foot and ankle at the following sites:
 

• Peninsula Health

• Frankston Private Hospital

	
 
• Holmesglen Private Hospital
 
• Cabrini Brighton Private Hospital
 
• Beleura Private Hospital
 
 
Patients who are unable to provide informed consent will not be enrolled in the study.

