#### **3.1.2 Secondary objectives**

Secondary objective:

1. to determine if vitamin C prevents CRPS in patients with lower limb extremity trauma in a dose-response manner

2. to determine the incidence of CRPS in lower limb extremity trauma.
3. To determine the demographics and characteristics of patients who develop CRPS of the lower limb

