### 6.2 Definitions

#### 6.2.1 Definitions for use in trials involving investigational medicinal products

##### Participant-specific adverse events

Adverse Event (AE): Any untoward medical occurrence in a patient or clinical trial participant administered a medicinal product and does not necessarily have a causal relationship with this treatment.

Adverse Reaction (AR): Any untoward and unintended response to an investigational medicinal product related to any dose administered.

Comment: All adverse events judged by either the reporting investigator or the sponsor as having a reasonable possibility of a causal relationship to an investigational medicinal product would qualify as adverse reactions. The expression ‘reasonable causal relationship’ means to convey, in general, that there is evidence or argument to suggest a causal relationship.

Serious Adverse Event (SAE) / Serious Adverse Reaction (SAR): Any adverse event/adverse reaction that results in death, is life threatening, requires hospitalisation or prolongation of existing hospitalisation, results in persistent or significant disability or incapacity or is a congenital anomaly or birth defect.

Note: Life-threatening refers to an event in which the participant was at risk of death at the time of the event. It does not refer to an event that hypothetically might have caused death if it were more severe.

---

Medical and scientific judgement should be exercised in deciding whether an adverse event/reaction should be classified as serious in other situations. **Important medical events** that are not immediately life-threatening or do not result in death or hospitalisation but may jeopardise the participant or may require intervention to prevent one of the other outcomes listed in this definition should also be considered serious.

Suspected Unexpected Serious Adverse Reaction (SUSAR): An adverse reaction that is both serious and unexpected. A SUSAR will be immediately reported to all stakeholders including the sponsor, investigators, HREC, local governance office and TGA.

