#### **9.2.2 Data Capture Methods and Storage**

Study investigators will be briefed on how to record information in their assessment and consultation notes for the trial as per the protocol using RedCap. Education material and training on the use of RedCap will be provided by the Principal Investigator.

Clinicians will document the following assessment criteria in RedCap at each two week, six week, twelve week and twenty-six week follow up point:

---

A: Does the patient report a history of:

- sensory changes (hyperaesthesia and/or allodynia)
- vasomotor changes (temperature asymmetry, skin colour changes and/or skin colour asymmetry)
- sudomotor/oedema changes (oedema, sweating change or sweating asymmetry)
- motor/trophic changes (decreased range of motion and/or motor dysfunction and/or weakness/tremor/dystonia and/or trophic changes of hair/nails/skin?)

---

B: Does the clinician observe:

- sensory changes (hyperaesthesia and/or allodynia)
- vasomotor changes (temperature asymmetry, skin colour changes and/or skin colour asymmetry)
- sudomotor/oedema changes (oedema, sweating change or sweating asymmetry)
- motor/trophic changes (decreased range of motion and/or motor dysfunction and/or weakness/tremor/dystonia and/or trophic changes of hair/nails/skin?)

---

C: Is there another diagnosis that better explains the signs and symptoms during today's history and examination?

Yes  
 No

---

D: Is the patient's pain disproportionate to the inciting event?

Yes  
 No

---

If the patient responds yes to three out of four questions in part A, AND the clinician observes two out of four signs in part B, AND answers yes to C and D, the patient meets the criteria for CRPS diagnosis.

Yes  
 No

Does the patient meet the criteria for CRPS diagnosis?

---

How has the patient felt since their last visit? (eg. fine, unwell, nauseated, in pain)

\_\_\_\_\_

---

Has the patient had any side effects to the medication such as abdominal upset, back pain, nausea or vomiting?

Yes  
 No

---

Has the patient taken the medication as prescribed?

Yes  
 No

The diagnosis of CRPS will be made if the patient meets the Budapest criteria, and patients will be referred to physiotherapy for pain management. The investigator will record whether the patients was diagnosed with CRPS in the EMR and communicate this back to the patient's General Practitioner via a clinical letter (this is standard practice in the event of a post-operative complication).

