### 11.3 Methods of analysis

The two secondary aims of this feasibility study will be addressed statistically. For the first secondary aim, diagnosis of CRPS will be ascertained in the form of time-to-event data, and rate ratios will be calculated using univariate Cox proportional hazards regression to directly compare diagnosis rates between the treatment and control groups.

Given the small sample size of this feasibility study, we anticipate randomization may inadequately balance the baseline characteristics of participants in the two treatment groups (e.g. age, trauma vs elective surgery). If necessary, a secondary set of analyses will be performed to adjust for baseline characteristics found to be imbalanced between groups to the extent of a 0.25 standard deviation difference in means (quantitative measures) or an odds ratio of 1.5 (binary measures). These analyses will be conducted using multivariate Cox proportional hazards regression models.

In the survival analyses, loss to follow-up will be considered a censoring event. This equates to an assumption that data is missing at random given the participant's treatment group and the timing of their loss to follow-up. The adequacy of this assumption will be checked in sensitivity analyses that will include both a multiple imputation by chained equations (MICE) approach and adjustment for baseline covariates predictive of propensity for dropout.

A sensitivity analysis will repeat the proportional hazards regression to compare rates of CRPS as diagnosed by the presence of individual Budapest criteria, rather than 3 out of 4 patient-reported symptoms or 2 out of 4 clinician-observed symptoms as required for formal CRPS diagnosis.

For the second secondary aim, the incidence risk of CRPS 6 months post surgery for lower limb extremity trauma patients will be reported as a proportion of the study sample.

Adverse events will be coded as per the Medical Dictionary for Regulatory Activities. Adverse events will be calculated at each visit, and patients may have more than one adverse event. Assessment of severity, frequency and relationship of adverse events to trial intervention will be presented by System Organ Class and information such as start date, stop date, severity, relationship expectedness, outcome and duration will be recorded. Adverse events leading to premature discontinuation from the trial intervention and serious treatment-emergent adverse events will be presented in a table.

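### An undefined disease-progression exception to the SAE rule could keep CRPS or operated-limb admissions out of the serious-event data

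*Protocol*

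**What the plan says.** Under the definitions for medicinal products (Protocol 6.2.1), one route to seriousness is that the event "requires hospitalisation or prolongation of existing hospitalisation". A separate, judgement-based route covers important medical events, including those that "may require intervention to prevent one of the other outcomes listed in this definition should also be considered serious".

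Protocol 6.5 modifies this with the exception "Hospitalisation due to progression of disease will not be considered an SAE for the purposes of this trial". The sentence appears twice in the section. After the second statement comes one further exception, "Elective surgery planned at the time of enrolment". The second statement refers to Section 8.1 for the definition of seriousness, but in the body of the protocol the definitions now stand under 6.2.

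The trial's purpose is preventive. Its first secondary objective (3.1.2) is "to determine if vitamin C prevents CRPS in patients with lower limb extremity trauma in a dose-response manner", and the synopsis states: "The outcome is development of CRPS at any stage following trauma or surgery within the six-month time frame". Under the methods of analysis (11.3), "serious treatment-emergent adverse events will be presented in a table".

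**The concern.** An exception for disease progression makes sense where participants enter with the disease under treatment and its worsening is expected. Here they enter after foot or ankle surgery or injury, and the capsules treat nothing present at entry. The protocol does not say which disease is meant. The candidates nearest to hand are CRPS, which is the clinical outcome, and the condition of the operated limb. Unplanned admissions for either are events that a safety review of this trial would want classified in the ordinary way.

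Seriousness is decided case by case by investigators, so an undefined term can be applied differently across the five sites. CRPS is also the outcome compared between arms, so admissions excepted on this ground need not be balanced between arms. An incomplete serious-event comparison could then be incomplete unequally. That last step is inference; the protocol gives nothing with which to size it.

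**Working it through.** The protocol attaches no figure to this rule, so there is nothing to reproduce. The check sets the relevant sections side by side.

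1. **Definition against exception.** Section 6.2.1 makes hospitalisation sufficient for seriousness. Section 6.5 withdraws that for one class of admission. The exception does not depend on relatedness, although 6.6 tells investigators always to suspect the trial product.

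2. **What disease could mean.** No definition is given. The text offers several candidates:
   - CRPS, the outcome. Section 9.2.2 handles it as a complication: informing the general practitioner of the diagnosis is described with the words "this is standard practice in the event of a post-operative complication".
   - Previous CRPS. It is collected as a baseline characteristic (3.2) and is not among the exclusions (4.4.2), so such patients can be enrolled.
   - The foot or ankle condition itself. The section on unscheduled visits (7.5.3) contemplates its exacerbation.
   - A comorbidity such as diabetes, also a listed baseline characteristic.

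   Nothing in the sections on capturing, documenting, assessing or reporting events (6.3 to 6.8) says that CRPS or operated-limb admissions remain SAEs.

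3. **Is the exception needed for planned surgery?** No. Elective surgery planned at enrolment has its own line.

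4. **What the SAE label controls.**
   - Reporting to the Sponsor-Investigator within 24 hours (6.8).
   - SUSAR status, which by definition requires a serious event (6.2.1), and with it reporting to the regulator (6.8).
   - The table of serious treatment-emergent events (11.3).

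5. **What survives without the label.** All adverse events are recorded whatever their relationship to treatment (6.4), and their severity, frequency and relationship are presented by System Organ Class (11.3). Death, life-threatening events, lasting disability and important medical events remain serious (6.2.1). A CRPS diagnosis is still captured as an outcome.

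6. **Time window.** Events are captured until 30 days after the final dose of a 50-day course (6.3): 50 + 30 = 80 days from the start of treatment. Follow-up is 26 weeks, or 26 × 7 = 182 days. The window is 80 / 182, about 44% of that length, so later admissions fall outside routine capture whatever the seriousness rule says.

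7. **Where an exemption could sit.** Section 6.8 already lists events exempt from expedited reporting (mild gastro-intestinal discomfort and mild discomfort on swallowing). The protocol therefore already has a place for a reporting exemption that leaves classification alone.

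**The case against.** The strongest reply is that, read strictly, the exception does not reach the events that matter. New-onset CRPS, wound infection and wound breakdown are new complications, not progression of anything, and the protocol itself treats CRPS as a complication. An admission suspected to be caused by the capsule would be an adverse reaction, not disease progression. The other seriousness criteria still catch the gravest cases. The events stay in the adverse-event data, and hospitalisation is asked about at every visit. CRPS is managed by referral to physiotherapy, and no admission for it is foreseen. In a feasibility study of about 100 participants, the reply concludes, one line defining the term would be enough.

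Most of this stands as a limit on reach. It does not remove the point. The strict reading is one of several that the wording permits, nothing tells the sites to adopt it, and the important-medical-event route depends on individual judgement.

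A reader might also infer that the two lists in 6.5 conflict. They do not: the second repeats the first and adds planned elective surgery. With the outdated cross-reference, this is duplication to tidy.

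**Conclusion.** The point holds as an ambiguity with consequences. A stated rule, whose key term is undefined and does not fit a prevention trial, allows CRPS or operated-limb admissions to lose SAE status whatever their relatedness. Where no other criterion applies, they would then be missing from expedited SAE reports, SUSAR assessment and the serious-event table. This rests on at least some investigators reading the exception broadly, which the text permits but does not require.

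The size cannot be estimated. The protocol gives no readmission rate and no basis for the share of admissions that would be labelled as progression. Several stronger conclusions are tempting but unsupported:

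- **That these admissions would be most of the SAE count.** The protocol's expectation of very low risk concerns the supplement and says nothing about all-cause admissions.
- **That the events are lost.** They remain recorded and tabulated as adverse events.
- **That the Independent Safety Monitor would not see them.** Section 10.1.3 does not limit the monitor to SAEs and defers to terms of reference that are not shown.
- **That the placebo's bacteria would create a hidden imbalance.** The protocol names the organisms without saying that they are live, and a suspected reaction to the capsule is not disease progression.

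**What to change.** Reconcile the SAE definition (6.2.1), the seriousness section (6.5) and the reporting section (6.8):

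- Delete the disease-progression exception in both places in 6.5.
- Keep a single list whose only exception is elective surgery already planned at enrolment.
- Replace the Section 8.1 reference with the current section number.
- If workload is a concern, name the expected admissions in 6.8 as exempt from 24-hour reporting, while keeping them classified and tabulated as SAEs.

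Merely defining the term would reduce the ambiguity, but would leave an exception with no evident use here. The cost is a short amendment and possibly a few more SAE forms.

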#### **6.6 Assessing the relatedness (causality) of a participant's AE**

All adverse events must have their relationship to trial intervention assessed by the investigator who evaluates the adverse event based on temporal relationship and his/her clinical judgment.

---

The degree of certainty about causality will be graded using the categories below. In a clinical trial, the trial product should always be suspected.

The relationship of the event to the trial intervention will be assessed as follows:

- **Unrelated:** There is no association between the trial intervention and the reported event. AEs in this category do not have a reasonable temporal relationship to exposure to the test product, or can be explained by a commonly occurring alternative aetiology.
- **Possible:** The event could have caused or contributed to the AE. AEs in this category follow a reasonable temporal sequence from the time of exposure to the intervention and/or follow a known response pattern to the test article, but could also have been produced by other factors.
- **Probable:** The association of the event with the trial intervention seems likely. AEs in this category follow a reasonable temporal sequence from the time of exposure to the test product and are consistent with the known pharmacological action of the drug, known or previously reported adverse reactions to the drug or class of drugs, or judgement based on the investigators clinical experience.
- **Definite:** The AE is a consequence of administration of the trial intervention. AEs in the category cannot be explained by concurrent illness, progression of disease state or concurrent medication reaction. Such events may be widely documented as having an association with the test product or that they occur after rechallenge.

## 6.7 Assessing the expectedness of a participant's AE

The investigator will be responsible for determining whether an adverse event (AE) is expected or unexpected. An AE will be considered unexpected if the nature, severity, or frequency of the event is not consistent with the risk information previously described for the trial intervention.

The severity of an Adverse Event will be assessed as follows:

- **Mild:** Events that require minimal or no treatment and do not interfere with the participant's daily activities.
- **Moderate:** Events that cause sufficient discomfort to interfere with daily activity and/or require a simple dose of medication.
- **Severe:** Events that prevent usual daily activity or require complex treatment.

## 6.8 Reporting of safety events

### Site Principal Investigator Reporting Procedures

The Site Principal Investigator/delegate is responsible for recording all safety events in the source document.

The Investigator is responsible for expedited reporting (within 24 hours of becoming aware of the event) to the Sponsor-Investigator the following local safety events:

1. USMs
2. SUSARs
3. All SAEs /SARs, except those that are identified below as expected in the trial population:

- 
- a. Mild gastro-intestinal discomfort
  - b. Mild discomfort when swallowing the capsule

The Site Principal Investigator is responsible for reporting SAEs (including SUSARs) to the Sponsor-Investigator as soon as possible but within 24 hours of the first knowledge of the event. These reports should be submitted using the trial Expedited Safety Report Form (see Appendix 3).

The Site Principal Investigator is also responsible for reporting SSIs, local USMs and local SUSARs to their research governance office within 72 hours of becoming aware of the event and in accordance with their local governance authorisation.

